8 DEMOGRAPHICS AND OTHER BASELINE CHARACTERISTICS

8.1 DEMOGRAPHICS

Baseline demographics and patient characteristics will be summarized in the evaluable, FAS, and PP populations including, age, sex, ethnicity, race, height, weight, and BMI. Categorical demographics will be summarized as frequency and percentage. Continuous demographics will be summarized by reporting n, mean, standard deviation, median, minimum, and maximum. A listing may also be generated.

8.2 PRIOR AND CONCOMITANT MEDICATIONS

Prior and concurrent medications use will be summarized as frequency and percent in the evaluable population. Prior and concomitant medication collection will be limited to erythropoiesis-stimulating agents (ESAs), intravenous iron, phosphate binders, calcimimetics, and anti-hypertensive medications (ACE inhibitors, ARBs, beta blockers, calcium channel blockers, central alpha agonists, and vasodilators [specifically, hydralazine and minoxidil]). A data listing may also be generated.

8.3 BASELINE MEDICAL AND SURGICAL HISTORY

Baseline medical and surgical history will be summarized in the evaluable population. The frequency and percent of patients will be summarized for each medical and surgical history attribute as either a current or past/resolved condition. Data listings will also be generated.

8.4 BASELINE PHYSICAL EXAM

Baseline physical exam will be summarized in the evaluable population. The frequency and percent of patients with a normal and abnormal results for each body system will be displayed. A data listing may also be generated.

8.5 DIALYSIS TREATMENT HISTORY

Baseline dialysis treatment history will be summarized in the evaluable population. The frequency and percent of patients will be summarized for each type of dialysis (hemodialysis – in facility, hemodialysis – home, peritoneal dialysis) they have received. A data listing may also be generated.

8.6 BASELINE VITAL SIGNS

Baseline vital signs, including blood pressure, pulse, and temperature (oral, tympanic, temporal), will be summarized in a table using n, mean, standard deviation, median, minimum, and maximum in the evaluable population. A data listing may also be generated.

8.7 BASELINE BIOCHEMISTRY LABS

Baseline biochemistry labs including, sodium, blood urea nitrogen, potassium, creatinine, bicarbonate, magnesium, phosphate, chloride, calcium, albumin, iron, transferrin saturation, total protein, ferritin, alkaline phosphate, parathyroid hormone, total iron binding capacity, AST (SGOT), and ALT (SGPT), will be summarized in a table using n, mean, standard deviation, median, minimum, and maximum in the evaluable population. A data listing may also be generated.

8.8 BASELINE HEMATOLOGY LABS

Baseline hematology labs including hemoglobin, hematocrit, white blood cell count, platelet count, and reticulocyte count, will be summarized in a table using n, mean, standard deviation, median, minimum, and maximum in the evaluable population. A data listing may also be generated.

All analyses of the primary effectiveness variable will be performed on the evaluable population with no missing value imputation, the FAS population with missing value imputation, and the PP population without missing value imputation. Analysis of both primary endpoints will exclude the transition phase treatment sessions due to the supervision of study staff, as it is believed these treatment sessions will not represent a true in-home treatment session.

The number of prescription changes occurring during the study is expected to be low. A summary table will be provided of all prescription changes by treatment period (in-center and in-home).

The study will be considered a success from a statistical standpoint if:

1. Both primary effectiveness variables pass their respective hypotheses, i.e., Ha0 and Hb0 above are rejected in favor of Ha1 and Hb1, respectively, and
2. The rate of adverse events per 100 treatments is not worse during the In-Home period as compared to the In-Center period. (see Section 10.1)

9.2 SECONDARY EFFECTIVENESS VARIABLES

Summary statistics (n, mean, standard deviation, median, minimum, and maximum) on the raw data as well as changes from baseline will be presented by timepoint for all endpoints shown below in the evaluable population for continuous variables. Categorical variables will be displayed as frequencies and percent. If multiple labs were performed at a given timepoint, the lab results from the date the site is basing clinical care from will be used and summarized in the analysis tables. All laboratory analysis will be performed by the local labs affiliated with the hemodialysis facility. Missing endpoints will not be imputed. Endpoints (with timepoint) include:

- Post-dialysis systolic blood pressure <90 mmHg or systolic blood pressure >180 mmHg following two consecutive treatments (C1, C2, C3, C4, C5, C6, C7, C8, T, H1, H2, H3, H4, H5, H6, H7, H8)
- Sodium (C1, C2, C4, C6, C8, H2, H4, H6, H8, Withdrawal)
- Urea (C1, C2, C4, C6, C8, H2, H4, H6, H8, Withdrawal; measured both immediately before and after each treatment)
- Potassium (C1, C2, C4, C6, C8, H2, H4, H6, H8, Withdrawal)
- Creatinine (C1, C2, C4, C6, C8, H2, H4, H6, H8, Withdrawal)
- Bicarbonate (C1, C2, C4, C6, C8, H2, H4, H6, H8, Withdrawal)
- Magnesium (C1, C2, C4, C6, C8, H2, H4, H6, H8, Withdrawal)
- Phosphate (C1, C2, C4, C6, C8, H2, H4, H6, H8, Withdrawal)
- Chloride (C1, C2, C4, C6, C8, H2, H4, H6, H8, Withdrawal)
- Calcium (C1, C2, C4, C6, C8, H2, H4, H6, H8, Withdrawal)
- Albumin (C1, C2, C4, C6, C8, H2, H4, H6, H8, Withdrawal)
- Iron (C1, C2, C4, C6, C8, H2, H4, H6, H8, Withdrawal)
- Transferring saturation (C1, C2, C4, C6, C8, H2, H4, H6, H8, Withdrawal)
- Total protein (C1, C2, C4, C6, C8, H2, H4, H6, H8, Withdrawal)
- Ferritin (C1, C2, C4, C6, C8, H2, H4, H6, H8, Withdrawal)
- Alkaline phosphatase (C1, C2, C4, C6, C8, H2, H4, H6, H8, Withdrawal)
- Parathyroid hormone (C1, C2, C4, C6, C8, H2, H4, H6, H8, Withdrawal)
- Total iron binding capacity (C1, C2, C4, C6, C8, H2, H4, H6, H8, Withdrawal)
- Aspartate transaminase (C1, C2, C4, C6, C8, H2, H4, H6, H8, Withdrawal)
- Alanine aminotransferase (C1, C2, C4, C6, C8, H2, H4, H6, H8, Withdrawal)
- Hemoglobin (C1, C2, C4, C6, C8, H2, H4, H6, H8, Withdrawal)
- Hematocrit (C1, C2, C4, C6, C8, H2, H4, H6, H8, Withdrawal)
- White blood cell count (C1, C2, C4, C6, C8, H2, H4, H6, H8, Withdrawal)
- Platelet count (C1, C2, C4, C6, C8, H2, H4, H6, H8, Withdrawal)
- Reticulocyte count (C1, C2, C4, C6, C8, H2, H4, H6, H8, Withdrawal)
- Ultrafiltration volume (net fluid removal) (All treatments)
- Number of alarms (All treatments)
- Time to resolve alarms (All treatments)
- Types of alarms (All treatments)
- Ability to deliver prescribed treatment
- Successful training of participant and caregiver (C4, C5, C6, C7, C8)
- Attempts required to complete training successfully (C4, C5, C6, C7, C8)
- Device deficiency assessment (All treatments and Withdrawal)
- Time to recovery after dialysis (TTR) (C1, H1, H4, H8, Withdrawal)
- EQ-5D-5L (C1, H1, H8, Withdrawal)
- Medical Outcomes Study (MOS) Sleep Index (C1, H1, H8, Withdrawal)
- Renal Treatment Satisfaction Questionnaire (C1, H1, H8, Withdrawal)
- Zarit Burden Interview (ZBI-12) (H8, Withdrawal)
- Edmonton Symptom Scale (ESAS-r) (C1, H1, H8, Withdrawal)

Estimates of secondary endpoints and differences measured between the last measurement (H8 or withdrawal) and the first measurement (C1) will be reported along with their two-sided 95% confidence intervals, as applicable. For continuous endpoints, we will derive the estimate of the difference in means and its 95% CI from a paired t-test for dependent samples. For dichotomous endpoints, we will derive the estimate of the difference in proportions and its exact 95% CI based on a score statistic. In terms of the PRO secondary endpoints, the total scores for EQ-5D-5L, MOS, and RTQS, as well as the per symptom scores on the ESAS-r will be descriptively analyzed. Finally, for TTR, the difference in rate and corresponding exact 95% CI (derived from a score statistic) between last measurement minus first measurement for each category (0-2 hours, 2-6 hours, 6-12 hours, 12-24 hours and >24 hours) will be shown. As these endpoints are not intended for labeling, the analysis will be descriptive in nature and therefore no type I error adjustment is required.

The analysis of the primary and secondary endpoints will exclude the data collected from the extended treatment phase (described in section 12.2).

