## 6.5 Study Structure

Following enrollment participants will begin hemodialysis treatments on the SC+ machine on a prescription of four-hour treatments, three times per week or per facility standard for a baseline period of 4 weeks within a hemodialysis facility administered by qualified dialysis clinical staff. During this time, both patients and caregivers will undergo extensive training and competency sign off. Competency, defined as three observed treatments without intervention or request for intervention from either the participant or their caregivers, will be assessed to ensure they are safe and proficient to conduct regular treatments in the home setting. This 4 week period can be extended week by week to a maximum of 8 weeks until competency sign off is achieved. If competency signoff is not achieved after 8 weeks, the participant will be withdrawn from the study. Following this in-clinic phase, a one-week transition phase of home hemodialysis will be provided with a dialysis professional present, followed by the home hemodialysis phase (test phase) without a dialysis professional present for an additional 8 weeks. Treatments in the transition and home hemodialysis phases will be performed by the participant and caregiver, 4 times per week, 3.5 hours each treatment.

Participants will undergo standardized physical examinations by a physician at the beginning of the in-clinic treatment phase (C1) and at the end of the self-care phase (H8) and at withdrawal. Regular physical exams, biochemistry, and hematology testing will be performed as defined below.

The study will be considered complete with regard to the primary objective after the minimum evaluable participants have completed the protocol and associated procedures defined below.

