6.2 EVALUABLE POPULATION (EVAL)

The evaluable population (EVAL) will include all participants who are enrolled in the study and who have successfully completed at least 75% of their dialysis treatments. A successfully completed dialysis treatment is defined as one completed as prescribed by the physician. The primary analysis population will be the evaluable population with no missing value imputation.

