13 SUMMARY OF CHANGES FROM THE PROTOCOL

The following table provides a list of changes from the protocol to the SAP, and the justification for each change. Any changes from the protocol made in the SAP will override the protocol.

Section	Description	Justification
Protocol Section 10.2.2 / SAP Section 4	Changing the number of subjects enrolled from 50 to up to 50	Clarifying that the trial will enroll up to 50 patients to obtain an evaluable sample size of 33 patients.
Protocol Section 10.3.1 / SAP Section 6.2	Updating primary analysis population to be the evaluable population rather than FAS	This decision ensures that patients will have data in both the in-clinic and in-home phases of the study which was an assumption of the power/SS calculations. The FAS does not ensure that patients will have data in both study phases.
Protocol Section 6.5 / SAP Section 7.7	Added 'unless otherwise pre-approved by sponsor' to the withdrawal if competency not achieved by C8	Sponsor will consider approving additional clinic time for participants that are competent on the SC+ but have not been deemed competent with another component of home training or whose homes were not prepared for device installation by the end of C8.
Protocol Section 10.6 / SAP Section 10.2	Changing methodology used to derive exact 95% CIs for difference in proportions from Clopper-Pearson to based on a score statistic	Clopper-Pearson is only used for exact 95% CI for a single proportion, not a difference in proportions. Exact 95% CIs based on a score statistic are more appropriate here.
Protocol Section 8.2 / SAP Section 7.7	Removing text regarding to be included in the data analysis, scheduled visits occurring after competency sign off must occur within +/- 3 days of the expected time point	This statement is not applicable to the statistical analysis due to the nature of the data collection and the frequency of visits in this study.

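### Treatment delivery and training success are planned in a population selected largely on treatment delivery, with no full-analysis-set version, so the reported figures will lean upward

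*SAP*

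**What the plan says.** SAP section 9.2 states that summary statistics "will be presented by timepoint for all endpoints shown below in the evaluable population for continuous variables". The next sentence, "Categorical variables will be displayed as frequencies and percent", names no population. The list that follows includes "Ability to deliver prescribed treatment", with no timepoint or phase, an entry that begins "Successful training of participant and caregiver (C4, C5, C6, C7, C8", and the attempts needed to complete training.

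SAP section 6.2 defines the evaluable population as enrolled participants "who have successfully completed at least 75% of their dialysis treatments", and adds: "A successfully completed dialysis treatment is defined as one completed as prescribed by the physician". It does not mention training. It does not say whether the 75% is taken of planned treatments or of treatments started before exit.

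SAP section 13 explains why the evaluable population replaced the FAS as the primary population: "This decision ensures that patients will have data in both the in-clinic and in-home phases of the study". Protocol section 6.5 says of training: "If competency signoff is not achieved after 8 weeks, the participant will be withdrawn from the study". SAP sections 7.7 and 13 let the sponsor pre-approve clinic time beyond C8. SAP section 7.2 reports FAS withdrawals by reason. No section plans training success or delivery on the FAS.

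**The concern.** An endpoint should not be summarised in a group chosen on that endpoint. A participant whose treatments repeatedly fall short of the prescription is removed from the figure meant to count those shortfalls. A participant who cannot be trained never reaches home and, on one reading of the 75% rule, leaves the training denominator too.

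Both questions matter for a home-use claim. Protocol section 5.4 treats it as critical to show that stable patients can be trained within a set number of weeks and then start at home. The reason SAP section 13 gives for the evaluable population is an assumption of the power calculation. That reason does not reach these two endpoints: they are descriptive (SAP section 7.5), and training success needs no home data.

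**Working it through.** The plan states no expected value for either endpoint. Its related figure is the evaluable sample in Protocol section 10.2.2, 33 participants with 32 home treatments each: 33 × 32 = 1056, which reproduces.

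**Inputs.** Clinic: 3 treatments per week for 4 to 8 weeks. Transition: 4 treatments in 1 week. Home: 4 per week for 8 weeks (Protocol section 2 footnotes and section 6.5). Entry rule: 75% (SAP section 6.2). Up to 50 enrolled for 33 evaluable (SAP section 4). Assumption: 3 clinic sessions per week, although the facility standard may differ.

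**Step 1: planned course and the 75% threshold.**

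| Clinic weeks | Clinic + transition + home | Total | 75% | Fewest home treatments if all clinic and transition ones are completed |
|---|---|---|---|---|
| 4 | 12 + 4 + 32 | 48 | 36 | 36 − 16 = 20, i.e. 20/32 = 62.5% |
| 8 | 24 + 4 + 32 | 60 | 45 | 45 − 28 = 17, i.e. 17/32 = 53.1% |

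If the delivery endpoint and the entry rule count the same thing, every evaluable participant is at or above 75% over the whole course, on either denominator. The last column shows that this floor does not carry over to the home phase.

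**Step 2: training, planned-treatment denominator.** A participant who fails after 8 clinic weeks has at most 24 treatments: 24/60 = 40%. Against the shortest course it is 24/48 = 50%. Both are below 75%, so the participant is not evaluable. The clinic frequency hardly matters: with x clinic treatments, x/(x + 36) ≥ 0.75 needs x ≥ 108, or 13.5 per week over 8 weeks.

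**Step 3: training, treatments-started denominator.** The same participant has 24/24 = 100% and is evaluable. Training success is then not forced to 100%. This reading conflicts with SAP section 13, because a clinic-only participant has no home data.

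**Step 4: how far training could be overstated on the planned denominator.** Non-evaluable: 50 − 33 = 17. If all 17 were training failures, true success is 33/50 = 66%. If instead the planned attrition comes off first (15% of 50 = 7.5, plus 2 deaths or transplants), 17 − 9.5 = 7.5 remain. About 7 training failures then fit, and true success is 43/50 = 86%. Either case reads about 100% in the evaluable population.

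**Step 5: selection effect on delivery (illustration only).** Assume 48 treatments, participant-level delivery rates from a beta distribution with a + b between 5 and 20, and identical definitions.

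| True delivery | Share evaluable | Delivery in evaluable population |
|---|---|---|
| 50% | 3–15% | 78–83% |
| 70% | 40–48% | 81–87% |
| 80% | 70–74% | 85–89% |
| 90% | 89–96% | 91–94% |

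The bias is small when delivery is good and large when it is poor.

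**Step 6: what the FAS would show.** Take 33 evaluable participants at 90% and 17 others at 0%, 50% or 74% (assumed), equally weighted. The FAS figure is (33 × 90 + 17 × r)/50 = 59%, 76% or 85%.

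**The case against.** A reader might infer that the entry rule requires success on both endpoints, so that they would read about 100% and at least 75% whatever the device does and neither could show failure. The documents do not support that.

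- The entry rule does not mention training, and its denominator is undefined. Exclusion of training failures follows only on the planned-treatment reading.
- Exceptions exist even on that reading. Protocol section 8.3 counts training as passed within 8 clinic weeks, while the SAP allows sponsor-approved time past C8. Such a participant could go home and be evaluable without having passed by C8.
- Success at C4 to C7 and the number of attempts can still vary and would show slow training.
- The entry rule and the delivery endpoint are not shown to be identical. The Protocol Appendix treats a failed treatment that is restarted as delivered, yet lists device-caused prolongation and prevented setups as reliability events. A session cut short for a reason unrelated to the device counts against evaluability.
- Delivery can range from 75% to 100% even with identical definitions. Against the 98.8% reliability rate in the sponsor's pilot study (Protocol section 5.6.2), 80% would look poor.
- The evaluable population is stated for continuous variables only, so it is not explicit for training success.
- FAS disposition reports withdrawals by reason, so training failures are not hidden.

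All of this stands and limits the claim. It does not remove the selection on delivery, and a disposition table is neither a training proportion nor a delivery rate. If the categorical sentence in SAP section 9.2 does not mean the evaluable population, the population for training success is undefined, which also needs correcting.

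**Conclusion.** The point holds in a limited form. For delivery, the selection follows from the text of SAP section 6.2. Its size depends on how far completion as prescribed and ability to deliver coincide, which the SAP does not settle. Because section 9.2 gives the delivery endpoint no phase, the home shortfall that could still be seen might be averaged away.

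For training, the conclusion is conditional on the planned-treatment reading. That is the only reading consistent with SAP section 13, but section 6.2 does not state it. The 66% is a bound that treats every non-evaluable participant as a training failure. It is not an estimate.

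Both endpoints are descriptive secondary endpoints outside the success criteria, so the trial's formal conclusion is unaffected. This is a cheap improvement in how two home-use results are reported. The argument does not extend to alarms or device deficiencies, which are not entry criteria.

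**What to change.** In SAP section 9.2, name the FAS as the population for training success, attempts to complete training, and ability to deliver prescribed treatments.

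- Training: use all participants who start C1 as the denominator, and count withdrawal before competency sign-off as not trained.
- Delivery: use all scheduled SC+ treatments up to exit, shown separately by phase.
- SAP section 6.2: state whether the 75% is of planned or of started treatments.
- Keep the evaluable-population tables as a supportive display.

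The cost is SAP wording and table shells, since the data are collected for all enrolled participants. The downside for the sponsor is that the reported figures may look less favourable.

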### **6.4 Participant Population and Numbers**

50 participants with established kidney failure undergoing hemodialysis will be enrolled to obtain 33 evaluable participants. Participants will have been receiving hemodialysis for at least 90 days, or in the case of peritoneal patients transitioning to hemodialysis, at least 90 days. Enrollment will include patients planning for home hemodialysis or currently on home hemodialysis or peritoneal dialysis. No more than 25% of participants will be recruited from a single site. No more than 40% of participants will be recruited who have received home hemodialysis during the 12 weeks preceding study entry.

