## 8.2 Visit Windows

In-clinic dialysis should start within 2 weeks after enrollment.

In-clinic dialysis sessions will be provided on Monday, Wednesday, and Friday (unless otherwise approved by Sponsor). In home dialysis sessions will be provided on Monday, Wednesday, Friday, and Saturday (unless otherwise approved by Sponsor).

Blood sampling will be performed on Wednesday (unless otherwise approved by Sponsor).

In-clinic dialysis will continue for a minimum of 4 weeks, and can be extended week by week to a maximum of 8 weeks until training competency is demonstrated. Timings for scheduled in facility visits will be calculated based on the date baseline completed. Treatment should occur at least three times per week as per standard protocol within the facility. The start of the transition phase will begin only after competency sign-off and will be 4 times during 1 week. The 8 week in home dialysis phase will begin after the transition phase and will be 4 times weekly for 8 weeks. To be included in the data analysis, scheduled visits occurring after competency sign-off must occur within  $\pm 3$  days of the expected time point.

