#### 10.6 Analysis of Secondary Endpoints

Summary statistics (n, mean, standard deviation, median, minimum and maximum) on the raw data as well as changes from baseline will be presented by timepoint for all labs shown below. If multiple labs were performed at a given timepoint, the lab results from the date the site is basing clinical care from will be used and summarized in the analysis tables. All laboratory analysis will be performed by the local labs affiliated with the hemodialysis facility.

A summary table of abnormal lab results will also be provided. All summary statistics (n, mean, standard deviation, median, minimum and maximum) will be computed relative to the lab results

that fell outside of specified ranges on the raw data. These ranges will be determined prior to data analysis.

For the PRO secondary endpoints, descriptive tests will be performed comparing last measurement (H8 or withdrawal) and first measurement (C1). Specifically, total score for EQ-5D-5L, MOS and RTQS will be compared using a 95% CI for the difference in last measurement minus first measurement. No descriptive test will be performed for the ZBI12, as it is only collected at the last study visit (H8 or withdrawal), however descriptive statistics will be displayed for the ZBI12. Similarly, the per symptom scores on the ESAS-r will be compared using a 95% CI. Finally, for TTR, the difference in rate and corresponding 95% Clopper-Pearson CI between last measurement minus first measurement for each category (0-2 hours, 2-6 hours, 6-12 hours, 12-24 hours and >24 hours) will be shown. As these endpoints are not intended for labeling, the analysis will be descriptive in nature and therefore no type I error adjustment is required.

Estimates of secondary endpoints and differences measured between the test and control periods will be reported along with their two-sided 95% confidence intervals.

Secondary safety endpoints will be analyzed in the same manner as the primary safety endpoint, as described in [Section 10.4.2](#).

Additionally, a table will be provided to show the number and percentage of the FAS subjects with at least one pre-specified AE by treatment period and overall for each dialysis treatment period (In-Center and In-Home), by MedDRA system organ class (SOC) and preferred term (PT). All AEs, all SAEs, and all device-related AEs will be summarized in a similar manner.

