7.7 TIMING OF ASSESSMENTS AND EVENTS FOR ANALYSIS

Patients will be considered enrolled in the study once they or their authorized representative have provided written informed consent and they have been documented to have successfully met all inclusion criteria and no exclusion criteria. In-clinic dialysis should start within 2 weeks of enrollment. Dialysis prescription during the in-clinic phase is 3 times per week, 4 hours per session. The in-clinic phase spans C1 through C4 at a minimum and continues for C5 through C8 until training competency is

established. Clinic visits will occur Monday, Wednesday, and Friday and blood sampling will be performed on Wednesday unless otherwise approved by sponsor. The start of the transition phase will begin the week after competency sign-off and the in-home phase will begin the following week. Dialysis prescription during the transition and in-home phases is 4 times per week, 3.5 hours per session. In-home visits will occur Monday, Wednesday, Friday, and Saturday unless otherwise approved by Sponsor. A participant will be automatically withdrawn if training competency is not achieved by C8, unless otherwise pre-approved by sponsor, or if treatments with SC+ cease for a period of more than 7 consecutive days during the course of the study or if 8 or more (non-consecutive) treatments are missed. Data taken prior to withdrawal will be included in study analyses.

C1 will be considered baseline for standard weekly Kt/V, as well as for biochemistry and hematology labs.

The baseline values for vital signs are the pre-dialysis measurements taken during the first treatment of C1.

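### For the laboratory endpoints, SAP 9.2 replaces the protocol's home-versus-clinic difference with last visit minus C1, does not declare it, and anchors it to a near pre-study value

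*SAP*

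**What the plan says.** Protocol 10.6 has a general sentence for the secondary endpoints: "Estimates of secondary endpoints and differences measured between the test and control periods will be reported along with their two-sided 95% confidence intervals". Protocol 6.5 shows which period is which. Home is the "home hemodialysis phase (test phase) without a dialysis professional present for an additional 8 weeks", and the clinic weeks before it are described as running "for a baseline period of 4 weeks within a hemodialysis facility administered by qualified dialysis clinical staff".

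SAP 9.2 has the matching sentence with a different contrast: "differences measured between the last measurement (H8 or withdrawal) and the first measurement (C1) will be reported", with two-sided 95% intervals, as applicable. Continuous endpoints use a paired t-test. SAP 7.7 adds: "C1 will be considered baseline for standard weekly Kt/V, as well as for biochemistry and hematology labs".

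SAP 13 says that changes made in the SAP override the protocol, and it tabulates them. Its only entry for Protocol 10.6 is the interval method for differences in proportions.

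On timing, Protocol 6.2.2 makes the laboratory samples pre-treatment. Protocol 8.2 puts clinic sessions on Monday, Wednesday and Friday, and states: "Blood sampling will be performed on Wednesday (unless otherwise approved by Sponsor". On prior treatment, Protocol 7.2.1 admits people from facility hemodialysis, from home dialysis at any frequency, and from peritoneal dialysis when moving to hemodialysis. Protocol 6.4 sets one limit on prior modality: "No more than 40% of participants will be recruited who have received home hemodialysis during the 12 weeks preceding study entry".

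**The concern.** The stated objective is SC+ at home compared with a hemodialysis facility. For phosphate, potassium, bicarbonate, BUN, hemoglobin and the other laboratory values, the interval that addresses this is home minus clinic within participant, on the same machine. The protocol promises that interval and the SAP does not produce it.

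No run-in on SC+ precedes C1. The C1 blood value therefore says little about SC+ in the clinic and much about what the participant was on before. Last visit minus C1 then combines a change of machine, for some participants a change of modality, and the change of setting. The later clinic samples (C4, and C6 and C8 when the phase is extended) are the ones that reflect weeks of in-clinic SC+, but they are not the reference for any difference.

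The substitution also reaches treatment-level measures recorded in both phases, such as ultrafiltration. There the issue is only the contrast. Carry-over in the blood does not apply.

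**Working it through.** The plan states no figure for this contrast, so there is none to reproduce. The check sets the texts side by side, counts sessions, and then shows the size under stated assumptions.

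**1. What each document compares**

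| Endpoint group | Protocol | SAP | Changed? |
|---|---|---|---|
| Laboratory values | Test vs control period; also change from baseline by timepoint (10.6) | H8 or withdrawal minus C1; also change from C1 by timepoint (9.2, 7.7) | Yes, not in SAP 13 |
| Ultrafiltration and similar | Test vs control period (10.6) | H8 or withdrawal minus C1, where applicable (9.2) | Yes, not in SAP 13 |
| Patient-reported outcomes | Last minus C1 (10.6) | Last minus C1 (9.2) | No |
| Secondary safety | As primary safety: home vs clinic (10.6) | As primary safety: home vs clinic (10.2) | No |

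**2. SC+ sessions before each clinic blood sample**

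With three sessions a week, a Monday start and a Wednesday pre-treatment sample, the count in week w is 3(w − 1) + 1, at day 7(w − 1) + 2 after the first session.

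- C1: 1 session, day 2
- C2: 4 sessions, day 9
- C4: 10 sessions, day 23
- C8: 22 sessions, day 51

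If the first session is itself on Wednesday, the C1 sample follows none.

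**3. Effect on the reported difference (assumed inputs)**

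Let d be the true shift in a laboratory value between the clinic and home regimens. Let p be the share of entrants already at home intensity, whose H8 value returns to their entry level. Let r be the fraction of that entry level still present at the reference sample. The group difference shown is d(1 − p·r).

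With complete carry-over (r = 1):

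- p = 0.20: 1 − 0.20 = 0.80, so 0.8d
- p = 0.40, the cap: 1 − 0.40 = 0.60, so 0.6d

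The cap is 0.40 × 50 = 20 participants if all 50 are enrolled.

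With first-order washout, r = 0.5^(days / half-life). The documents give no half-life, so 2, 7 and 30 days are assumptions. With p = 0.40:

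| Half-life | r at C1 | H8 − C1 shows | r at C4 | H8 − C4 shows |
|---|---|---|---|---|
| 2 days | 0.50 | 0.80d | 0.00 | 1.00d |
| 7 days | 0.82 | 0.67d | 0.10 | 0.96d |
| 30 days | 0.95 | 0.62d | 0.59 | 0.76d |

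C4 is the better reference at each of these half-lives, but it is not free of carry-over for slow markers. Former peritoneal dialysis patients add a change of modality whose size and direction the documents do not give.

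**4. Precision of the alternatives**

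The plan's correlation of 0.5 for Kt/V is borrowed here, as AR(1) or as compound symmetry. Samples are C1, C2, C4, H2, H4, H6 and H8, at weeks 1, 2, 4, 7, 9, 11 and 13 (transition in week 5). SDs are in units of one value's SD.

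- H8 − C1: AR(1) √[2(1 − 0.5¹²)] = 1.41; compound symmetry √[2(1 − 0.5)] = 1.00.
- H8 − C4: AR(1) √[2(1 − 0.5⁹)] = 1.41; compound symmetry 1.00.
- Home mean − clinic mean: AR(1) 0.92, from summing the correlation matrix over those weeks; compound symmetry √[0.5(1/3 + 1/4)] = 0.54.

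Moving the reference from C1 to C4 costs no precision. Period means narrow the interval by a factor of about 1.5 to 1.9, but the clinic mean includes C1 and C2. At a 7-day half-life it retains (0.82 + 0.41 + 0.10)/3 = 0.44 of the entry level, against 0.10 at C4.

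**The case against.** Several points on the other side stand, and they set the scope.

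- A reader might infer that every secondary contrast was switched. It was not. SAP 10.2 keeps the home-versus-clinic GEE model for the secondary safety endpoints. For patient-reported outcomes nothing was replaced, because the protocol already says that "descriptive tests will be performed comparing last measurement (H8 or withdrawal) and first measurement (C1").
- A reader might infer that the later clinic samples go unused. SAP 9.2 presents raw values and changes from baseline at each timepoint, so C4, C6 and C8 do appear. What is missing is a home-minus-clinic difference with an interval, because each of those changes is measured from C1.
- A reader might infer that someone who withdraws during the clinic phase supplies a clinic value as the last measurement. SAP 9.2 uses the evaluable population, which must have completed at least 75% of treatments (SAP 6.2). A participant leaving after six clinic weeks has at most 18 sessions of 18 + 4 + 32 = 54 planned, or 33%. SAP 6.2 does not define its denominator, but SAP 13 states the intent that evaluable participants have data in both phases.
- For entrants from facility hemodialysis, C1 does reflect a clinic setting, though mostly on another machine.
- The 0.6d figure needs the 40% cap filled, all of those entrants at about study home intensity although any frequency is allowed, and full carry-over.
- The endpoints are descriptive (SAP 7.5) and outside the success rule (SAP 9.1).

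None of this supplies the missing interval or explains why the protocol's contrast was dropped.

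**Conclusion.** The point holds for the laboratory endpoints and, as to the contrast only, for treatment-level measures recorded in both phases. The SAP replaces the protocol's period comparison without declaring it. For laboratory values the replacement is anchored to a sample taken after about one SC+ session, against ten before C4, assuming a Monday start.

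The size is not known from the documents. If 20% to 40% of entrants were already at home intensity and showed no change, the reported difference would be about 0.8d to 0.6d. That is an assumed upper range of attenuation, not an estimate. The error could also differ in size or direction for people coming from another facility machine or from peritoneal dialysis.

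The primary endpoints and the success rule are untouched. The change should be made because it restores the protocol's own comparison at almost no cost, not because the trial's conclusion depends on it. Nor would a home-minus-clinic difference isolate setting: the prescription also moves from 3 × 4 h (or facility standard) to 4 × 3.5 h a week.

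**What to change.** In SAP 9.2, for laboratory values and for treatment-level measures recorded in both phases:

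1. Add a within-participant home-minus-clinic difference with a 95% interval, in participants with at least one home value. Name one definition in advance: last home value minus last in-clinic value (C4, or C6 or C8 if extended), or home-period mean minus clinic-period mean. The first leaves less carry-over and suits the laboratory values. The second is more precise and suits ultrafiltration, where blood carry-over does not arise.
2. Keep H8 minus C1 as a second column, labelled *change from study entry*.
3. State beside the table that home minus clinic combines the change of setting with the change from 3 × 4 h to 4 × 3.5 h.
4. Record the change from Protocol 10.6, with its reason, in SAP 13.

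The patient-reported and secondary safety analyses need no change on this account.

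The cost is SAP wording and one extra table column. All the samples are already scheduled. Participants without a home value leave this contrast but stay in the by-visit summaries.
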